#### **Exploratory outcomes measures:**

Exploratory outcomes will be analyzed similarly to the primary and secondary outcomes and include:

1. Self-reported physical activity scores measured at baseline, midpoint and 12 weeks assessed via GODIN Physical Activity Questionnaire.
2. Self-reported subjective norms, attitudes (both instrumental and affective attitudes – see below) perceived behavioral control, and intentions at baseline and 12 weeks via Theory of Planned Behavior Questionnaire. (4,5)

##### Instrumental attitudes:

- Useless–useful
- Unimportant–important
- Worthless–valuable
- Not worthwhile–worthwhile
- Harmful–beneficial

##### Affective attitudes:

- Unsatisfying–satisfying
- Unpleasant–pleasant
- Not enjoyable–enjoyable
- Boring–exciting
- Not fun-fun

#### **SENSITIVITY ANALYSIS:**

To explore robustness of the primary outcome, we will perform the following sensitivity analyses:

- We will perform sensitivity analyses on the primary outcome (change in HbA1c at 12 weeks) and secondary outcomes
  - including study site (UOW, UBC) as a covariate,
  - stratified by study site (UOW, UBC).
  - Per protocol analyses based on adherence to eating a compliant breakfast (i.e., uploaded daily breakfast photo that complies with group allocation, taking a conservative approach that if no photo is uploaded the breakfast did not comply) including only those participants who remained in the trial and had >80% adherence
  - Sub-analyses based on or controlling for breakfast egg intake

Secondary endpoints exploring within-group changes from baseline will be performed using a linear mixed model. The model will include fixed effects for timepoint (Baseline vs Week 6/12), stratified allocation factors (sex), site and random effects for participants to account for participant variability in the outcome measures.

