## Research Method

Eighty-two (N=82) individuals between University of British Columbia and University of Wollongong, Australia with physician diagnosed T2D (HbA1c < 8.5%), between the ages of 20-79 years, with a BMI above 25 kg/m^2 will be recruited through online social media and newspaper advertising. REACH BC and Trialfacts will assist with recruitment. REACH BC is an initiative of BC's health authorities and partner universities bridging the gap between the public and researchers. Trialfacts combines extensive marketing and advertising expertise with in-depth clinical trial experience to create effective marketing solutions. We have a partnership with the Kelowna Diabetes Program to assist recruiting from >6500 well-monitored T2D patients in our region.

**Inclusion criteria** will be: i) physician-diagnosed T2D of  $\geq 1$  year; ii) current HbA1c of <8.5%; iii) BMI: higher than 25kg/m^2; iv) blood pressure of <160/99 mm Hg assessed according to guidelines; v) non-smoking; vi) not on hormone replacement therapy, corticosteroids, or anti-inflammatory medications; and vii) 20–79 years old. **Exclusion criteria will include:** i) Use of exogenous insulin; ii) taking more than 2 glucose lowering medications; iii) ongoing medical treatment for diseases such as cancer, auto-immune or inflammatory disease, liver or kidney disorders; iv) allergy, intolerance or aversion to eggs or any other dietary restrictions (e.g., vegan, breakfast skipping) that will prevent them from following the standardized study diets; v) being unable to follow remote guidance by internet or smartphone; vi) being unable to follow the controlled diet instructions;.

Based on our previous studies ~55% of males and ~70% of females with T2D who volunteer will meet these eligibility criteria so we anticipate no recruitment issues. We will allow statins and anti-hypertensive medications if on a stable dose for 3 months because the majority of T2D patients are on at least one of these medications; excluding them would leave a small pool for recruitment and limit the generalizability of our findings.

A 3-month parallel-group randomized controlled trial is proposed. Eligible participants will be randomized to either the Low-carb High-fat breakfast (LCHF, n=41) or a low-fat “standard care” control breakfast (CTL, n=41), to be consumed daily for a period of 3 months.

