## **SAMPLE SIZE CONSIDERATIONS**

We used a previous breakfast intervention in T2D along with our recently published one-day egg-based low-carbohydrate (LC) breakfast trial to calculate the sample size for this RCT. Rabinovitz et al  compared a “big breakfast” containing higher fat and protein providing 33% total daily energy to a small breakfast providing 12.5% daily energy over 3 months in a similar sample of participants with T2D using a similar parallel-group design. They reported an absolute reduction in HbA1c% of 0.46% in the big breakfast group. This is similar to the magnitude of change observed in a recent study by Nichols et al  who reported an average HbA1c reduction of 0.45% in response to metformin, the standard prescribed medication for people newly diagnosed with T2D. For this reason, it is reasonable to use the study published by Rabinovitz et al to estimate a clinically relevant effect size for our sample size calculation. A medium effect size (Cohen’s  $d = 0.46$ ) was calculated from the Rabinovitz study. In agreement, for our recent one-day study examining an egg-based LC breakfast (3), the effect size (Cohen’s  $d$ ) for improvements in CGM-derived glucose control variables (including AUC, iAUC, glycemic variability, and mean) ranged from  $d = 0.48-1.2$ .

Taking a conservative approach, we used an effect size of  $d = 0.4$  in the sample size calculation. The total sample size necessary to detect a between-within interaction using a repeated measures ANOVA with an effect size of  $d = 0.4$  (which corresponds to an ANOVA effect size  $f = 0.2$ ) with 90% power and 5% type 1 error with a conservative correlation among repeated measures of  $r = 0.5$  is 68 ( $n = 34$  per group, calculated using G\*Power v3.1.9.2). To account for a 20% dropout rate (2), we aimed to recruit a sample size of  $n = 41$  per group. These calculations were documented in the original grant application (Feb 2019), trial protocol (Dec 6, 2019), and SAP (Nov 17, 2021).

Adjustment as of 16th January 2022:

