## **ANALYSIS OBJECTIVES, OUTCOMES, AND STATISTICAL METHODS**

All data were collected longitudinally. Statistical analysis will be performed blinded to participant allocation after the last participant has completed the trial.

**Primary endpoint:** The prespecified primary outcome for this trial will be a comparison of the change in HbA1c (in the standard percentage units) from baseline to 12 weeks between the dietary intervention groups.

The analysis of the primary outcome is based on a superiority approach (i.e., we expect that the LC intervention will be superior in leading to decreased HbA1c compared to the CTL intervention). Data will be analyzed by constrained longitudinal data analysis (cLDA) via a linear mixed model with fixed effects for timepoint (baseline and week 12), the interaction between timepoint and dietary intervention group, and stratified allocation factors (sex) as well as random effects for participants to account for the correlation of repeated measures within participants.

The cLDA approach constrains the baseline means to be equal between the treatment groups, which is a reasonable assumption in the context of a randomized controlled trial. If a participant does not have any HbA1c recordings in the end of the trial, only the baseline value of that participant will be included in the model and no post-intervention value for that participant will be included. No missing data will be imputed as per contemporary guidelines. Model specification will be assessed visually using normal probability plots and residuals vs. fitted values plots. Models will be run using log-transformed outcome variables when departure from model assumptions is observed.

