**Secondary outcome measures:** To supplement the primary outcome of A1c, continuous glucose monitors (CGMs) will be worn by participants during the first and last 14 days of the intervention (i.e., both timepoints of CGM will be collected while participants are consuming their allocated breakfast). Changes in CGM variables (fasting glucose, mean glucose, maximum glucose, minimum glucose, 24-h area under the curve, incremental area under the curve, MAGE, SD, time below 3.9 mmol/L, time above 10mmol/L , time in range (3.9-10 mmol/l); 2-hour post-meal: incremental area under the curve, mean glucose, maximum glucose and SD will be calculated for each 14 day period. CGM data will be analyzed using a linear mixed model that will include fixed effects for timepoint (First 14 days vs Last 14 days), group (LC vs. CTL), their interaction, and stratified allocation factors (sex) and random effects for participants. In this analyses the main effect of group will be most important to identify an overall effect of the intervention on glycemic control variables.

Continuous secondary outcomes will be analyzed similarly to the primary outcome using a constrained baseline longitudinal data analysis linear mixed model (with all relevant follow-up timepoints included as a fixed factor in the model). Secondary outcomes include:

1. Changes in self-reported satiety and fullness assessed with a 100 mm visual analogue scale (VAS) on satiety and fullness at baseline, midpoint and 12 weeks, which were based on those validated by Flint et al. (1).
2. Changes in self-reported dietary intake (total kilocalories, grams of carbohydrates and percent of total calories, grams of protein and percent of total calories and grams of fat

and percent of total calories, egg consumption) assessed via self-report (3-day dietary records) at baseline, midpoint and 12 weeks.

3. Changes in self-reported body weight and body mass index from baseline to 12 weeks.
4. Changes in blood markers (fasting insulin, high-sensitivity C-reactive protein, triglycerides, total cholesterol, HDL, LDL and VLDL) from baseline to 12 weeks.
5. Changes in carotenoid levels (lutein and zeaxanthin) from baseline to 12 weeks.
6. Changes in cognitive function from baseline to midpoint and 12 weeks.

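### The SAP's model for within-group change lists no group term: fitted to pooled data it does not estimate within-group change, and fitted by arm it need not agree with the between-group analysis

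*SAP*

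**What the plan says.** The SAP's main inference is between groups. Its section on analysis objectives and methods defines the primary endpoint as a "comparison of the change in HbA1c (in the standard percentage units) from baseline to 12 weeks between the dietary intervention groups". The primary model is a cLDA with a timepoint effect plus "the interaction between timepoint and dietary intervention group, and stratified allocation factors (sex) as well as random effects for participants". For the other outcomes, "Continuous secondary outcomes will be analyzed similarly to the primary outcome using a constrained baseline longitudinal data analysis linear mixed model". CGM variables have their own mixed model with group, timepoint and their interaction.

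A further analysis closes the Sensitivity Analysis section: "Secondary endpoints exploring within-group changes from baseline will be performed using a linear mixed model". Its terms are given as follows: "The model will include fixed effects for timepoint (Baseline vs Week 6/12), stratified allocation factors (sex), site and random effects for participants". Neither group nor a timepoint-by-group interaction is listed.

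The SAP does not say whether this model is fitted to all participants or to each arm, whether it yields p-values or only estimates, or how its results relate to the between-group contrast.

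**The concern.** There are two problems, one of specification and one of interpretation.

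The specification does not produce the quantity it names. A model without group cannot separate the arms unless it is fitted to each arm in turn, and the SAP does not say that. If it is fitted by arm, it drops the common-baseline constraint of the cLDA. The report could then show an LC change, a CTL change and a between-group effect that do not reconcile.

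On interpretation, within-arm change mixes any diet effect with regression to the mean, season and the effect of being in a trial. If each arm's change were given a significance verdict, a reader could set a significant fall in LC beside a non-significant one in CTL and call it a diet benefit, even when the between-group test is negative. Comparing two within-arm p-values is not a test of the difference between the diets.

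**Working it through.** **Inputs from the documents.**
- 34 analysable participants per arm (SAP, Sample Size Considerations).
- 5% type 1 error and r = 0.5 (same section). Sidedness is not stated, so two-sided is assumed.
- 1:1 allocation (Protocol, Research Method).
- 31 complete pairs per arm at January 2022 (SAP, adjustment of 16 January 2022).

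**Not in the documents.** The SD of change and the size of any change shared by both arms are not given. Shared change is therefore shown over a range, as d in units of the SD of change.

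**1. The plan's own figure.** For the repeated-measures interaction with two groups and two times, λ = f²·N·m/(1−r) = 0.04 × 68 × 2/0.5 = 10.88 on F(1, 66). Power is 0.9015 at N = 68 and 0.893 at N = 66, so 68 (34 per arm) reproduces. It is used here only for the arm size.

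**2. The model fitted to pooled data.** With equal arms and complete pairs, the timepoint coefficient is (Δ_LC + Δ_CTL)/2. It equals each arm's own change only if the two changes are the same.

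**3. The model fitted by arm.** Assume complete pairs and equal variance at both times.
- The difference between the two arm-specific changes is (follow-up difference) − (baseline difference).
- The cLDA effect is (follow-up difference) − r × (baseline difference).
- The gap is therefore (1−r) × (baseline difference) in size. Its SD is 0.5 × √(2/34) = 0.12 outcome SD, or 0.5 × √(2/31) = 0.13 at 31 per arm.
- Against the planning d = 0.4, 0.12/0.4 is about 30%.

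Precision also differs. In outcome-variance units, an arm's change has variance 2(1−r)/n = 1/n from the by-arm model. As a cLDA contrast it has variance (1−r²)/n + (1−r)²/(2n) = 0.75/n + 0.125/n = 0.875/n, about 12% lower.

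**4. Within-arm verdicts with no diet difference.** Both arms have the same true change d. The within-arm power p comes from the noncentral t with 33 df and noncentrality d√34, and p_up is its part in the direction of improvement. The arms are independent, so P(LC improved, CTL not significant) = p_up(1−p) and P(exactly one arm significant) = 2p(1−p). With n = 34:

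| Shared change d | p | LC only | Exactly one arm |
|---|---|---|---|
| 0 | 0.050 | 2.4% | 9.5% |
| 0.2 | 0.205 | 16% | 33% |
| 0.3 | 0.397 | 24% | 48% |
| 0.343 | 0.493 | 25% (maximum) | 50% |
| 0.4 | 0.620 | 24% | 47% |
| 0.5 | 0.808 | 16% | 31% |
| 0.6 | 0.924 | 7% | 14% |
| 0.8 | 0.995 | 0.5% | 1.0% |

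For scale, a shared fall of 0.15-0.25 HbA1c points with an SD of change of 0.5-0.7 gives d from 0.15/0.7 = 0.21 to 0.25/0.5 = 0.50. These HbA1c values are assumptions.

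With 31 per arm, LC only is 15% at d = 0.2, 24% at 0.4, 18% at 0.5 and 9% at 0.6.

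**5. Comparison with the proper test.** In 200,000 simulated trials per setting, the two-sample test of the difference in change rejected in 4.9-5.1% whatever the shared change, so about 2.5% in favour of LC. At n = 34, LC-only significance without a significant between-group test occurred in 16.1 − 2.1 = 14.0% of trials at d = 0.2, 24.9 − 2.3 = 22.6% at d = 0.343 and 19.3 − 2.2 = 17.1% at d = 0.46.

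**The case against.** The strongest reply is that the misuse is not in the plan. The SAP speaks of exploring within-group changes. It does not promise p-values, does not say the two arms' results will be compared, and does not propose to infer benefit from them. The hypotheses, the primary endpoint and the continuous secondary analyses are all comparisons between diets, and for CGM the SAP names the group effect as the most important term. This stands. A reader might infer that the plan prespecifies a claim of improvement in LC but not in CTL, or that the trial's error rate is compromised. The documents support neither.

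Four further points are fair:
- The rate in step 4 depends on a window of shared change that includes the mathematical maximum. Outside that window the pattern is rare, so the figure must carry its condition.
- The sentence begins with secondary endpoints and mentions week 6, while HbA1c is measured only at baseline and week 12. It may therefore not cover HbA1c at all. The table is in SD units and applies to any continuous outcome with two measurements.
- A reader might count site, which the primary model omits, as a further defect. Site is constant within a participant and has no interaction with time. With complete pairs it leaves the timepoint estimate unchanged, and incomplete pairs could shift it only slightly. It is not a defect worth raising.
- The cLDA contrast is not identical to the by-arm change. It is measured from the common constrained baseline and not from that arm's own observed baseline.

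None of this repairs the missing group term or the possible mismatch with the cLDA effect.

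**Conclusion.** The concern holds in a limited form. The within-group model as listed does not define a within-group change unless it is fitted by arm. Fitted that way, its two changes can differ from the cLDA effect by an amount with SD of about 0.12 outcome SD (34 per arm, r = 0.5, complete pairs). The planned between-group tests remain valid and keep their error rate.

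The interpretive risk is conditional on within-arm p-values being reported and on both arms sharing a change of about 0.2-0.5 SD of change. Then LC alone is significant in about 16-25% of trials with no diet difference, roughly 6 to 10 times the 2.5% for the between-group test favouring LC. This is worth correcting because the plan already has a model that gives coherent within-arm changes.

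**What to change.** Delete the separate within-group model. For each outcome analysed by cLDA, report each arm's change from baseline with a 95% confidence interval as a contrast from that same model. Show it beside the between-group contrast, label it descriptive, and give no within-arm p-value. Add one sentence saying that diet effects are judged only on the between-group contrast.

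Because the contrast is change from the common baseline, tabulate the observed baseline and follow-up means by arm alongside. CGM has no pre-intervention period in the SAP, so any within-arm CGM change should come from its own group-by-timepoint model and be described as first versus last 14 days.

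The cost is a few lines of SAP wording and one small table. There is one model fewer to fit, and no effect on data collection or recruitment.

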## HANDLING OF MISSING DATA AND OTHER DATA CONVENTIONS

No statistical imputations will replace missing data for the outcome measures (*data as observed*). However, the constrained baseline longitudinal data analysis – in a linear mixed model with restricted maximum likelihood – is a principled approach to addressing missing outcome data, including the baseline value of the continuous outcome measure. The model permits the inclusion of all participants in the analysis with either a baseline or a follow-up value. Thus, missing data will not be imputed for the ITT analyses. If a blood marker value is below the detection limit, we will explore the results following imputation of the value as limit of detection (LOD) divided by the square root of 2 (6).

